## e. Statistical Design and Power

**1. Power and Sample Size Determination:** Power to detect changes in PCr:tP between groups is our primary determinant of sample size in the R61 phase because of the centrality of spectroscopic findings in our hypotheses. In another study, after 8-weeks of oralCr, adult female methamphetamine users had significantly increased PCr levels with a standardized effect size of

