0.920. In an open-label study in depressed adolescents. PCr levels following Cr administration increased by 6.2%+ 9.6%. In a dose-finding study of Cr compared to placebo, the effect size for differences in PCr levels between the group receiving 4 grams of Cr daily compared to placebo was 0.7. We hypothesize that supplementation with Cr with or without 5-HTP will increase frontal cortical PCr levels. P-MRS neuroimaging will be performed at baseline, and repeated after 8 weeks of treatment with Cr + placebo, 5-HTP + placebo, or 5-HTP + Cr. To address our first hypothesis, a population-averaged generalized estimating equation (GEE) regression model is used for group comparison of the  $\Delta PCr$  (PCrWEEK 8 - PCrBASELINE) associated with Cr + placebo, 5-HTP + placebo, or 5-HTP + Cr. We will control for age, gender, and tissue partial volume effects (i.e., gray matter, white matter and cerebrospinal fluid) for in vivo phosphorus metabolite measurements made at two time points. The GEE for each subject, i has the form Yi(t)=Xi  $\beta$  +  $\epsilon_i$ , where Yi and Xi represent measured metabolite (PCr or  $\beta$ -NTP) levels and design matrix of covariates, respectively. The error term follows a multivariate normal distribution:  $\varepsilon_i \sim N(0, V_i)$ , where Vi is the variance of metabolite levels. We assume that measures taken closer to each other in time are more highly correlated than those taken further apart. Therefore, the first-order autoregressive structure, AR(1) is assumed such as  $cov[\varepsilon_i(t), \varepsilon_j(t')] = \rho^{|t-1|}$ tVi to model the dependence of the correlation on repeated measures from the same participant, where t is time variable and p is the correlation coefficient between the clinical symptom measures of two successive assessments. Assuming  $\rho = 0.30$ , expected MDES = 5% across the groups, and harmonic mean SD = 10%, respectively, a sample size of 60 participants (15 per group; 4 aroups) and 2 neuroimaging time points per participant has >80% power using the AR (1) GEE model at the 0.05 alpha level. In our open-label study, we experienced ~20% participant attrition. Imputation of missing data cannot be utilized for neuroimaging data. Therefore, anticipating a 20% attrition rate, we propose a target enrollment of 75 participants for the R61 phase.

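### The >80% power that sets the sample size cannot be reproduced: for a 5-point group difference in PCr change, two-sided power is 36–48% (pooled Cr v no Cr) or 20–26% (any two arms)

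*Combined protocol and SAP*

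**What the plan says.** Section e (Statistical Design and Power), item 1, opens by giving this calculation its role: "Power to detect changes in PCr:tP between groups is our primary determinant of sample size in the R61 phase". The hypothesis is directional and covers both creatine arms: "We hypothesize that supplementation with Cr with or without 5-HTP will increase frontal cortical PCr levels". The analysis is a GEE group comparison of the change in PCr from baseline to week 8, with an AR(1) working correlation.

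The power statement sets the correlation at 0.30 and continues: "expected MDES = 5% across the groups, and harmonic mean SD = 10%, respectively, a sample size of 60 participants", at 15 per group in four groups. It concludes that this number with "2 neuroimaging time points per participant has >80% power using the AR (1) GEE model at the 0.05 alpha level". The 60 are completers: enrolment is raised to 75 for 20% attrition, and 60/(1 − 0.20) = 75 is correct.

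Four inputs are left open:
- **Sidedness** of the 0.05 level.
- **Contrast:** pooled creatine arms, pairs of arms, or an overall test. The model description names only three arms and omits double placebo, while the sample size counts four.
- **Scale of the 10% SD.** The model's variance term "is the variance of metabolite levels", which suggests an SD of levels. The one percentage SD cited from earlier work is of a change: "PCr levels following Cr administration increased by 6.2%+ 9.6"%.
- **Correlation.** It is defined as the "correlation coefficient between the clinical symptom measures of two successive assessments", although it is applied to two PCr scans.

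**The concern.** A 5-point effect against a 10-point SD is half an SD. Detecting half an SD between two independent groups with 80% power takes about 64 per group. Here the largest groups that can be formed are 30 and 30. A second scan does not close that gap when the outcome is a change and the between-scan correlation is only 0.30, because subtracting a weakly correlated baseline adds variance.

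This figure is the stated reason for the trial's size. A reader who accepts it would believe that a true 5-point creatine effect has less than a 20% chance of being missed, and would give a non-significant result more weight than the design can bear.

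**Working it through.** **Inputs** (all from section e, item 1): difference 5 points; SD 10 points; ρ = 0.30; α = 0.05; 15 completers per arm, hence 30 v 30 when the two creatine arms are pooled against the other two. Assumption: age, gender and tissue covariates remove no variance (tested in step 5).

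**Step 1. SD of the change.** With two scans, AR(1) is a single correlation, and the group effect in the GEE is the group difference in change.
- If 10 is the SD of a level: 10 × √(2 × (1 − 0.30)) = 10 × √1.4 = 11.83.
- If 10 is already the SD of the change: 10.

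**Step 2. Attempt to reproduce >80%.** Noncentrality = 5 / (SD × √(1/n₁ + 1/n₂)), with n₁ + n₂ − 2 degrees of freedom. For 30 v 30:
- SD 11.83: standard error 11.83 × √(2/30) = 3.06; noncentrality 5/3.06 = 1.64; two-sided power 36.3%.
- SD 10: standard error 2.58; noncentrality 1.94; two-sided power 47.8%.

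| Comparison, 5-point difference in change | SD 11.83: two-sided (one-sided) | SD 10: two-sided (one-sided) |
|---|---|---|
| Any two arms, 15 v 15 | 20% (30%) | 26% (38%) |
| Pooled Cr v 5-HTP + placebo, 30 v 15 (the three named arms) | 26% (37%) | 34% (46%) |
| Pooled Cr v no Cr, 30 v 30 | 36% (49%) | 48% (61%) |
| Four-group F-test, means 0, 0, 5, 5 | 23% | 32% |

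No entry reaches 80%.

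**Step 3. What does exceed 80%.**
- A two-sided pre-post test of a 5-point rise pooled over arms: 79–91% in the 45 participants of the three named arms, 90–97% in all 60. This compares no groups.
- A one-sided pre-post test in the 30 creatine participants with SD 10: 85%. Again, no group comparison.
- A one-sided 30 v 30 comparison with the two scans treated as independent observations (SD 10/√2 = 7.07): 86%. This is not the change.
- 5/10 read as Cohen's f = 0.5 in a four-group F-test: noncentrality 60 × 0.25 = 15, power 90%. With two creatine and two other arms, f = (difference/2)/SD, so the difference is 2 × 0.5 × 10 = 10 points.

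**Step 4. What the design can detect.** For two-sided 80% power at 30 v 30 the difference must be 8.7 points (SD 11.83) or 7.4 points (SD 10). For 5 points, 89 or 64 per compared group would be needed. The expected 95% confidence interval half-width at 30 v 30 is 2.00 × 3.06 = 6.1 points or 2.00 × 2.58 = 5.2 points, so an estimate of zero would not exclude 5.

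**Step 5. Could correlation or covariates rescue the figure?** Two-sided 80% power for 5 points at 30 v 30 needs a change SD of about 6.8.
- From a level SD of 10, this requires ρ = 1 − 6.8²/200 ≈ 0.77, not 0.30.
- Otherwise covariates must remove 1 − 6.8²/10² ≈ 54% of the variance (SD 10) or 1 − 6.8²/140 ≈ 67% (SD 11.83).
- Adjusting for baseline PCr, which the plan does not list, gives SD 10 × √(1 − 0.30²) = 9.54 if 10 is a level SD: 51.5% two-sided, 64% one-sided, 80% two-sided at 7.0 points.
- If 10 is the change SD, the level SD is 10/√1.4 = 8.45 and the adjusted SD is 8.45 × √0.91 = 8.06: 66% two-sided, 77% one-sided, 80% two-sided at 5.9 points.

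**The case against.** The strongest reply is that the 5% may never have been meant as a difference between creatine and no creatine. The sentence speaks of an effect across the groups and stresses 60 participants with two scans. The resting-state power statement (item 3) also uses all 60 in a repeated-measures comparison with baseline. A pre-post calculation of that kind does exceed 80%. On this view the fault is a calculation that answers the wrong question, not an arithmetic slip. That may explain where the figure came from, but it does not support it: item 1 says the power is for changes between groups, and the analysis it describes is a group comparison.

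Other points have some force:
- **Larger effects are cited.** Item 1 mentions standardized effects of 0.920 and, against placebo, 0.7. At 30 v 30 two-sided these would have 94% and 76% power, so the pooled design is not weak for effects that large. The power statement, however, uses 5/10.
- **Covariates are planned:** "We will control for age, gender, and tissue partial volume effects". No variance reduction is claimed for them, and step 5 shows how large it would have to be.
- **The endpoint is unsettled.** The opening sentence powers PCr:tP, while the hypothesis and model concern PCr. This should be cleared up, but does not alter arithmetic done in percentages.
- **It is a proof-of-concept study.** A small trial is acceptable. That is a reason to keep the sample size, not to keep an unsupported power figure.

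**Conclusion.** The stated power does not follow from the stated inputs for the comparison the plan names. For a 5-point difference in PCr change with 60 completers, two-sided power is 36–48% for pooled creatine against no creatine, the most favourable of the between-group contrasts examined, and 20–26% for any two arms. The chance of missing such an effect with the pooled contrast is 52–64%. One-sided testing reaches at most 61%. Baseline adjustment, which is not in the plan, reaches at most 66% two-sided or 77% one-sided.

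The ranges come from the undefined SD. They assume that the 5% is a group difference in change, that 60 complete both scans, and that the other covariates remove no variance. Confidence is high because every reading of the planned change comparison that was tried falls short of 80%. Since this number is the stated primary basis for the sample size, it must be corrected.

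**What to change.** Keep 60 completers and amend section e, item 1:

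1. **Name the contrast.** Pooled creatine against no creatine (30 v 30) fits the hypothesis. State the sidedness, and whether the measure is PCr or PCr:tP.
2. **Define the inputs.** Say whether 10% is the SD of a level or of the change, and define ρ as the correlation of PCr between the two scans.
3. **Replace >80%** with the matching two-sided figure for the planned comparison:
   - 10% as the SD of a level: 36% for 5 points, 80% at 8.7 points.
   - 10% as the SD of the change: 48% for 5 points, 80% at 7.4 points.
4. **Report the creatine effect with a 95% confidence interval**, so that a non-significant result is read against its width.

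Option: adjust for baseline PCr, which is already collected. Because the GEE as written has both scans as outcomes, this means making the change or the week 8 value the outcome and moving baseline to the covariates. With 10% as a level SD, the plan could then state about 51.5% for 5 points and 80% at about 7.0 points; with 10% as the change SD, about 66% and 5.9 points.

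Cost: wording only for items 1–3 if the planned comparison is kept, and a small analysis change with no new data if baseline is added. No extra participants are needed. The stated power becomes less favourable, and naming one contrast commits the team to it.

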2. Analysis of P-MRS Data: To analyze study data, a raw Hamming filter will be applied before performing 2D fast Fourier transformation, and each free induction decay (FID) will be linebroadened with 10 Hz of apodization. After Fourier transformation and frequency shift correction. zero-/first-order phase correction and baseline correction with polynomial interpolation will be applied. Spatial filtering with a Hamming window function will be implemented to reduce signal contamination from neighboring voxels. The preprocessed P-MRSI data will be fitted using jMRUI software with the Advanced Method for Accurate, Robust and Efficient Spectral (AMARES) fitting algorithm. Metabolites of interest include PCr, β-NTP, tP, and their ratios. From registered anatomical images, tissue segmentation will be performed using FSL (FMRIB's Software Library) software so that cerebrospinal fluid (CSF)-corrected metabolite concentrations as well as gray matter percentage in each voxel can be used as covariates in the analysis. Generalized estimating equations regression modeling will be used to evaluate group differences in metabolite levels controlling for age, sex, education level, and tissue partial volume effects (i.e. gray matter, white matter, CSF). Subjects with MDD will be compared to HCs at baseline and at follow-up. Sub-group analyses by gender will be included given evidence that Cr has been proposed as especially effective in women. Fisher's exact test will be used to compare groups on categorical variables.

**3. Analysis of Resting State Data:** As is seen in the small cohort of pilot data, we anticipate treatment groups to demonstrate increased global connectivity of the subgenual ACC after treatment, among other changes. A recent analysis determined that we can achieve single subject reproducibility of FC metrics of 0.16 Fisher-transformed correlation units. If we conservatively set the effect size at 8% and SD at 9% of mean, a sample size of 60 depressed subjects would achieve >90% power to detect significant treatment effects with the repeated measures design compared to baseline. For FC analyses, 361 regions of interest (ROIs) comprising a parcellation of cortical gray matter will be compared between placebo and active treatment subjects. We

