**4. Analysis of 5-HT Levels:** There is limited data available regarding the effect of twice-daily oral 5-HTP supplementation on whole blood 5-HT levels in subjects with MDD taking ADs. Estimates of whole blood (platelet) serotonin levels in MDD vary widely, including values from  $119 \pm 52.9$  ng/ml (n=30) to  $169.5 \pm 74.5$  ng/ml (n=29) to  $203.2 \pm 59.3$  ng/ml (n=25), suggesting that whole blood 5-HT levels average roughly  $161 \pm 62$  ng/ml in subjects with MDD. A sample of 60 subjects with MDD allocated 1:1 between 5-HTP (5-HTP+Cr and 5-HTP+placebo) and placebo (Cr+placebo and placebo+placebo) would have, in a t-test of means, >70% power to detect an effect size of 0.8. This effect size would be equivalent to an increase in average 5-HT levels to roughly those seen in non-depressed subjects. Although this is a relatively large effect size, it is consistent with findings related to the effect of oral tryptophan supplementation (at 50mg/kg/day in non-depressed men) which found an estimated effect size of 1.1. This analysis assumes that creatine supplementation will not independently affect circulating serotonin levels, though there is no data regarding this to our knowledge. 5-HT levels will be analyzed using linear mixed models with repeated (before and after) measures, controlling for gender, age, group allocation, antidepressant use, oxygen saturation, and other confounds.

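### The plan asks whether creatine works better in women but specifies only sub-group analyses by gender and no treatment-by-sex interaction, so the stated method does not test the stated question

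*Combined protocol and SAP*

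**What the plan says.** Section e (Statistical Design and Power) gives the same sentence at the end of item 2 (31P-MRS) and near the end of item 3 (resting-state data): "Sub-group analyses by gender will be included given evidence that Cr has been proposed as especially effective in women". Neither item says how the sub-group results will be compared or interpreted.

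Elsewhere in section e, sex is an adjustment variable:

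- Item 1, GEE for the change in PCr: "We will control for age, gender, and tissue partial volume effects".
- Item 2, GEE for metabolite levels: "controlling for age, sex, education level, and tissue partial volume effects".
- Item 4, mixed model for serotonin: "controlling for gender, age, group allocation, antidepressant use, oxygen saturation, and other confounds".

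The documents name no interaction with sex, no rule for declaring a sex difference, no exploratory label and no multiplicity control specific to the sex sub-groups. They give no expected sex ratio. Randomization is blocked, and no stratification by sex is stated.

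**The concern.** The reason given for the sub-group analyses concerns effect modification: creatine may do more in women than in men. A main-effect covariate for sex removes average differences between women and men but forces the creatine effect to be the same in both. Splitting the sample gives one estimate per sex but no test of their difference. If one sex reaches 0.05 and the other does not, the contrast may reflect only chance or the size of each sub-group.

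This matters more than usual here for two reasons. With 60 completers the sub-groups are small, so disagreement between them is common under equal effects. The plan also names the expected direction in advance, so a chance 'women only' result would look like confirmation of a prior hypothesis.

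**Working it through.** **Inputs from section e, item 1.** Effect: "expected MDES = 5% across the groups". Spread: "harmonic mean SD = 10" (per cent). Correlation between scans 0.30; alpha 0.05, taken as two-sided; 60 completers, 15 per group. A cited dose-finding study gives a standardized effect of 0.7 for creatine against placebo.

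**Assumptions, not in the documents.** The two creatine arms are pooled against the two arms without creatine (30 v 30). The sex split is the same on both sides: 50:50 (15 women, 15 men per side) or 2:1 (20 women, 10 men per side). Unadjusted t-tests on the change in PCr stand in for the GEE.

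**Step 1. Standardized effect.** If 10% is the SD of the change, d = 5/10 = 0.50. If it is the SD at each scan, the SD of the change is 10 × √(2 × (1 − 0.30)) = 11.83%, so d = 5/11.83 = 0.42.

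**Step 2. The plan's own figure.** The plan says the sample "has >80% power using the AR (1) GEE model at the 0.05 alpha level". By noncentral t, a between-group contrast has power of 20% (d = 0.42) or 26% (d = 0.50) at 15 v 15, and 36% or 48% at 30 v 30. The stated figure is therefore not reproduced for such a contrast. It is exceeded, for example, if 5% is read as the SD of the four group means (f = 5/10 = 0.5, power 90%). The sex point does not depend on settling this; Step 4 covers the case where overall power is exactly 80%.

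**Step 3. Same true effect in both sexes.** With n per side in one sex, the noncentrality is d × √(n/2) on 2n − 2 degrees of freedom. Call the resulting powers Pw (women) and Pm (men). The sub-groups are independent, so P(women only) = Pw × (1 − Pm) and P(neither) = (1 − Pw) × (1 − Pm).

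| d | Women:men per side | Pw | Pm | Women only | Men only | Neither |
|---|---|---|---|---|---|---|
| 0.42 | 15:15 | 0.20 | 0.20 | 16% | 16% | 64% |
| 0.50 | 15:15 | 0.26 | 0.26 | 19% | 19% | 54% |
| 0.70 | 15:15 | 0.46 | 0.46 | 25% | 25% | 30% |
| 0.42 | 20:10 | 0.26 | 0.15 | 22% | 11% | 64% |
| 0.50 | 20:10 | 0.34 | 0.19 | 28% | 12% | 54% |
| 0.70 | 20:10 | 0.58 | 0.32 | 40% | 13% | 29% |

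Worked row (d = 0.50, 20:10): noncentrality is 0.5 × √10 = 1.58 in women and 0.5 × √5 = 1.12 in men. Then 0.338 × (1 − 0.185) = 0.275, or 27–28%.

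**Step 4. Sensitivity.** If the true effect gave exactly 80% power at 30 v 30 (d = 0.74), 'women only' would occur in 25% of trials at 50:50 and 41% at 2:1. For a pairwise 15 v 15 contrast with 8 women and 7 men per arm it is 11% (d = 0.42), 13% (0.50) and 20% (0.70). With 10 women and 5 men per arm it is 13%, 17% and 27%.

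**Step 5. Interaction test under the same equal effects.** It rejects in 5% of trials over both directions (simulated 4.9–5.1%), so about 2.5% favour women.

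**Step 6. Power of the interaction.** Suppose men have no effect. The noncentrality is d / √(2/nw + 2/nm) on 56 degrees of freedom. At 15:15 and d = 0.70 this is 0.70/0.516 = 1.36, power 27%. At 20:10 and d = 0.42 it is 0.77, power 12%. At 24:6 and d = 0.42, power falls to 10%.

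**The case against.** The strongest reply is that the plan promises only to include sub-group analyses. Sex-specific estimates with confidence intervals would fit that sentence, and nothing excludes an interaction test. This is a proof-of-concept study sized on the overall spectroscopy comparison, and the sex analysis is a secondary element. Much of this stands, and it limits what can be claimed:

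- A reader might infer that the plan will judge sex differences by comparing significance between women and men. No such rule is written. The defect is that no test of the difference is specified, so the rates above are conditional on that comparison being made.
- A reader might infer that a false 'women only' finding is likely, or the expected pattern. It is not. At the SDs that follow from section e, item 1, neither sex is significant in 54–64% of trials. In the pooled comparison, 'women only' passes one half only with about 80% women and an effect of about 0.7 or more.
- A tilt towards women needs more women than men. The documents give no sex ratio, and at 50:50 the error falls equally on either side.
- The rates come from a PCr t-test. They do not carry over to the connectivity analysis, which applies false discovery rate control across 361 × 361 connections.
- A reader might infer that a spurious sex finding would steer the next phase. The documents tie no decision to sex.

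The reply does not remove the mismatch between question and method. The plan's own rationale calls for a comparison between the sexes, and no model in the plan makes one.

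**Conclusion.** The concern holds in a limited form. The plan raises a differential-effect question and names a method that cannot answer it. If sub-group significance were compared under an identical 5% effect, 'women only' would appear in about 16–19% of trials at 50:50 and 22–28% at 2:1. At the cited effect size of 0.7 the figures are about 25% and 40%. The like-for-like rate for an interaction test is about 2.5%. This is a substantial minority risk, and its size rests on the assumed sex split, the pooled creatine contrast, a two-sided 0.05 level and unadjusted t-tests. Pairwise contrasts give lower rates. For the resting-state analysis the gap in method is the same, but no rate is claimed.

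**What to change.** - **Item 2 (31P-MRS):** add a creatine-by-sex interaction to the GEE fitted to all participants. If the response is the metabolite level at two scans rather than the change, this is the creatine-by-sex-by-time term with its lower-order terms. Report the interaction and the sex-specific estimates from that model, each with a 95% confidence interval.
- **Item 3 (resting state):** add the corresponding treatment-by-sex term to the group-wise ANOVA, under the same false discovery rate control.
- **Both items:** state that a sex difference will be claimed only from the interaction, and that the analysis is exploratory.

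The cost is one model term and a sentence or two in each item, with no extra participants or data. The downside is low power: roughly 10–27% for effects of 0.42–0.7 even if creatine does nothing in men. The report should say so, and should not read a non-significant interaction as evidence that the sexes respond alike.

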will conduct a second level of analysis using eight networks delineated as follows and derived from Gordon *et al.*: auditory, salience, frontoparietal, default, dorsal attention, ventral attention, sensorimotor, and visual. Two levels of analysis will be performed to balance multiple comparisons and granularity of spatial information. For each pair of 8 networks, mean BOLD time series will be extracted across the entire network and Fisher-transformed correlation coefficients will be calculated. An acceptable false discovery rate (q < .05) over all pairs of networks will be assumed to denote significant partial correlation with diagnosis. To evaluate which connections are anticorrelated, we will use an independent dataset for an unbiased estimate obtained from the S1200 Release of the Human Connectome Project (HCP) dataset. Group-wise ANOVA will be performed with false discovery rate correction for multiple comparisons across 361 x 361 connections tested for treatment group differences in FC before and after treatment compared to placebo group. Sub-group analyses by gender will be included given evidence that Cr has been proposed as especially effective in women. Subjects with MDD will be compared to HCs at baseline and at follow-up.

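### The >90% connectivity power rests on an unsourced SD of 9% of the mean, not reconciled with the cited 0.16 Fisher-unit reproducibility, and does not carry over to the active-versus-placebo comparison

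*Combined protocol and SAP*

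**What the plan says.** All of this is in the combined protocol and SAP, section e. Statistical Design and Power, item 3 (Analysis of Resting State Data), unless noted.

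- **Hypothesis:** "we anticipate treatment groups to demonstrate increased global connectivity of the subgenual ACC after treatment". This is a summary score for one region.
- **Precision figure:** "we can achieve single subject reproducibility of FC metrics of 0.16 Fisher-transformed correlation units". The text does not say that 0.16 is an SD, nor which metric or scan length it belongs to.
- **Power inputs, in the next sentence:** "If we conservatively set the effect size at 8% and SD at 9% of mean". There is no source for either percentage, no mean connectivity, and no statement of whether the SD is between subjects, per visit or of the change.
- **Power claim:** "a sample size of 60 depressed subjects would achieve >90% power to detect significant treatment effects with the repeated measures design compared to baseline".
- **Planned analyses:** a comparison of placebo with active-treatment participants over 361 regions; a network level at which "mean BOLD time series will be extracted across the entire network and Fisher-transformed correlation coefficients will be calculated"; and a connection level: "Group-wise ANOVA will be performed with false discovery rate correction for multiple comparisons across 361 x 361 connections tested", for treatment-group differences relative to placebo. Some connections are expected to be negative: "To evaluate which connections are anticorrelated, we will use an independent dataset for an unbiased estimate".
- **Group sizes (item 1, Power and Sample Size Determination):** "a sample size of 60 participants (15 per group; 4" groups).

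**The concern.** The only precision figure for connectivity is in Fisher units, and the power inputs that follow it are percentages of an unstated mean. A reader cannot convert one to the other, so nothing supports calling the inputs conservative. If 0.16 describes the error of the quantity tested, the total SD cannot be smaller than 0.16, and 9% would then require very strong mean connectivity.

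There are two further mismatches. A percentage of the mean is not a workable scale for single connections whose means may be near zero or negative. And the power is quoted for change from baseline in all 60 participants, placebo included, whereas the planned comparisons are between groups.

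At stake is how far the connectivity results can be trusted in either direction. With >90% on record, a null result could be given more weight than the placebo comparison can bear.

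**Working it through.** **Inputs.** From the plan: effect 8%, SD 9% of mean, N = 60, 15 per group, reproducibility 0.16. Assumed: two-sided alpha 0.05 (0.05 is stated only for the PCr calculation; sidedness is not stated). Mean connectivity is not given, so a range is shown. Power is from the noncentral t distribution, with noncentrality d√n for one sample and d√(n₁n₂/(n₁+n₂)) for two.

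**1. The plan's own figure.** d = 8/9 = 0.889. Pre-post test, n = 60: power >99.9%. If 9% is a per-visit SD with no correlation between visits, d = 0.889/√2 = 0.629 and power is 99.8%. So >90% holds on the stated inputs for the test the sentence describes.

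**2. What 9% would need if 0.16 is the SD of the tested metric.**
- Mean z = 0.16/0.09 = 1.78, which is r = tanh(1.78) = 0.94.

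**3. What >90% power would need.** For a pre-post test with n = 60, 90% power needs d = 0.425, so the SD can be at most 8/0.425 = 18.8% of the mean.
- SD 0.16: mean z ≥ 0.16/0.188 = 0.85 (r = 0.69).
- SD of change 0.16 × √2 = 0.226: mean z ≥ 0.226/0.188 = 1.20 (r = 0.83).

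The threshold for the power claim is therefore 0.85 (or 1.20). The 1.78 tests only the 9% input.

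**4. Pre-post power at assumed means.** d = 0.08 × mean z / SD, n = 60. Between-subject variation in response is ignored, which favours the plan.

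| Mean z | 0.16 as % of mean | d, SD 0.16 | Power | d, SD 0.226 | Power |
|---|---|---|---|---|---|
| 0.3 | 53% | 0.150 | 21% | 0.106 | 13% |
| 0.5 | 32% | 0.250 | 48% | 0.177 | 27% |
| 0.8 | 20% | 0.400 | 86% | 0.283 | 58% |

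**5. Single connections.** At a mean of z = 0.1, an effect of 8% is 0.008 and an SD of 9% is 0.009 Fisher units, about one-eighteenth of 0.16 (0.16/0.009 = 17.8). At a mean of zero both vanish, and below zero the percentages have no sensible meaning. One pair of percentages cannot describe a matrix whose means run from positive to negative.

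**6. Between-group power on the plan's own 8% and 9%.** Here 9% is taken as the SD of change, and no multiplicity correction is applied.
- All active v placebo, 45 v 15: noncentrality 0.889 × √(45 × 15/60) = 2.98; power 83%.
- One active arm v placebo, 15 v 15: noncentrality 0.889 × √(15 × 15/30) = 2.43; power 65%.
- Four-group ANOVA: 67% if one group differs from the other three by 8%, 81% if two do.
- If 9% is instead a per-visit SD, with the correlation of 0.30 assumed for PCr, the SD of change is 9 × √(2 × 0.70) = 10.6% and the two contrasts fall to 70% and 51%.
- A 30 v 30 contrast, such as all creatine arms against the rest, reaches 92%, but item 3 does not name that comparison.

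False discovery rate control over the connection matrix would lower the power for any single connection further.

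**The case against.** The strongest reply is that no contradiction can be shown. The 0.16 comes from a cited source and is called a reproducibility, not an SD. If it were a 95% repeatability limit, for instance, the within-subject SD would be 0.16/2.77 = 0.058, and 9% would need a mean of only 0.058/0.09 = 0.64. If it is already the SD of a test-retest difference, multiplying by √2 counts the error twice. Mean connectivity appears nowhere. The hypothesis also concerns a regional average: with independent errors of 0.16 per connection, averaging about 13 connections at mean z = 0.5, or 35 at 0.3, brings the SD down to 9%, and a region has up to 360.

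This stands. A reader might infer that 0.16 rules out 9%, or that >90% fails on every reading; the documents support neither. Nor is it an arithmetic slip, since the stated inputs give the stated power. It is also fair that the power sentence is not expressly tied to single connections, that connectivity does not set the sample size (item 1 names PCr:tP as the primary determinant), and that nothing in the plan says a null result will be read as no effect.

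It does not rescue the figure. The plan gives no error for the averaged score, connections sharing one seed region share its noise (so more than 13 or 35 would be needed), and averaging does not remove between-subject variation. Averaging over connections is not available for the connection-level test. The between-group shortfall does not depend on how 0.16 is read.

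**Conclusion.** The concern holds in a limited form. The SD of 9% and the word conservative are unsupported and unreconciled with the one precision figure cited. Two parts are firm:

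- A percent-of-mean effect and SD cannot serve the single-connection analysis.
- On the plan's own inputs the active-versus-placebo comparison has 83% power (45 v 15) or 65% (15 v 15) before multiplicity correction, not >90%. This assumes two-sided alpha 0.05 and 9% as the SD of change.

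One part is conditional. If 0.16 is the repeat-scan SD of a single tested connection, >90% pre-post power for an 8% effect needs mean z of at least 0.85, or 1.20 if the SD of change is 0.226. Whether the claim holds for an averaged subgenual ACC score cannot be judged from the documents. The plan should be corrected, but neither the design nor the sample size is called into question by this point.

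**What to change.** In item 3, name the connectivity metric on which the power claim rests, give its SD of change and the target difference in Fisher units with their source (pilot data or the repeat-scan data behind 0.16), and say what the 0.16 measures. Recompute and restate the power for the between-group test with its actual group sizes, and state how multiplicity is handled.

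If no SD of change is available for the chosen metric, delete the >90% statement, give the minimum detectable difference for the planned N (in Fisher units, or SD units if need be), and label the connectivity results exploratory.

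The cost is wording and a recalculation. The stated power will probably be less favourable. No change to design, visits or recruitment is needed.
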